The Taper Period (up to 4 weeks, depending on dose level achieved) will be required for subjects who complete the study or withdraw from treatment during the study if the following doses are achieved: LCM ≥ 3 mg/kg/day for subjects receiving oral solution, or LCM ≥ 150 mg/day for subjects taking tablets; lower doses will not require a taper (refer to Section 7.2.2). A Taper Visit must be completed at the end of the Taper Period. Taper of LCM may not be required for some subjects who complete the study or withdraw from the study prematurely, depending on the treatment option selected by the investigator in consultation with the subject and/or legal representative(s) or for subjects who participate in EP0151 or EP0152.

End of study and Safety Follow-Up Period

Subjects who complete the study or withdraw prematurely from the study, and who discontinue use of LCM, should complete a Safety Follow-Up Visit 2 weeks (± 2 days) after the final dose of LCM. A Safety Follow-Up Telephone Contact is required for all subjects (those who complete the study as planned or have withdrawn prematurely from the study). This telephone contact will occur 30 days (-1/+3 days) after the final dose of LCM. The Safety Follow-Up Visit and the

Safety Follow-Up Telephone Contact are not required for subjects who participate in EP0151 or EP0152.

Unscheduled visits may be conducted at the discretion of the investigator.

Detailed schedules of study procedures are provided in Section 5.2, and a study schematic diagram is included in Section 5.3.

No formal interim analysis or Data Monitoring Committee is planned.

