^s Lacosamide for taper will be dispensed only for subjects who achieve a dose of LCM ≥ 3 mg/kg/day (oral solution) or LCM ≥ 150 mg/day (tablet). It is recommended that the dose be tapered gradually in weekly decrements. A slower taper is permitted, if medically necessary. In case of an emergency, a faster taper is permitted after discussion with the Medical Monitor, whenever possible. Taper of LCM may not be required for some subjects who withdraw from the study prematurely, depending on the treatment option selected by the investigator in consultation with the subject and/or legal representative(s).

^t Subjects and/or legal representative(s) will be reminded to complete the diary on a daily basis.

^u Ongoing AEs from the primary study will be followed, as well as recording of new AEs during the current study.

Table 5-2: Schedule of study assessments: Treatment Period from Week 32 to Week 96/Termination Visit

Assessments	Treatment Period ^a													ETV ^b	Unsch Visit ^c	
	TC6	V7	TC7	V8	TC8	V9	TC9	V10	TC10	V11	TC11	V12	V13 / TermV ^d			
	W32	W36	W40	W44	W48	W52	W56	W60	W66	W72	W78	W84	W96			
Concomitant medications	X	X	X	X	X	X	X	X	X	X	X	X	X	X	X	X
Concomitant AEDs	X	X	X	X	X	X	X	X	X	X	X	X	X	X	X	X
VNS assessment ^e		X		X		X		X		X		X	X	X	X	X
Physical exam (complete)						X							X	X		
Physical exam (brief)		X		X				X		X		X				
Tanner Stage ^f						X							X	X		
Blood pressure and pulse rate (including orthostatic assessments in ambulatory subjects)		X		X		X		X		X		X	X	X	X	X
Body weight and height		X		X		X		X		X		X	X	X	X	X ^g
Head circumference						X				X			X	X		
Neurological exam (complete)						X							X	X		
Neurological exam (brief)		X		X				X		X		X				
12-lead ECG ^h						X				X			X	X		
Clinical chemistry and hematology blood sample						X				X			X	X		

Table 5-2: Schedule of study assessments: Treatment Period from Week 32 to Week 96/Termination Visit

Assessments	Treatment Period ^a													ETV ^b	Unsch Visit ^c
	TC6	V7	TC7	V8	TC8	V9	TC9	V10	TC10	V11	TC11	V12	V13 / TermV ^d		
	W32	W36	W40	W44	W48	W52	W56	W60	W66	W72	W78	W84	W96		
Endocrinology blood sample						X				X			X	X	
Urinalysis (subjects aged ≥5 years) ⁱ						X				X			X	X	
Serum pregnancy test ^j						X				X			X	X	
Urine pregnancy test ^j		X		X				X				X			
C-SSRS ^k		X		X		X		X		X		X	X	X	X ^l
Clinical GIC						X				X			X	X	
Caregiver GIC						X				X			X	X	
Achenbach CBCL ^m						X				X			X	X	
Bayley-III ⁿ						X				X				X	
BRIEF/BRIEF-P ^o						X				X			X	X	

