5.4 Rationale for study design and selection of dose

Epilepsy is a condition for which an improved benefit/risk ratio for medicinal products remains a challenge; this is especially true for pediatric patients.

EP0034 will provide continued availability of LCM to subjects who have completed SP0969, which is a Phase 3, multicenter, double-blind, randomized, placebo-controlled, parallel-group study to evaluate the efficacy and safety of LCM as adjunctive therapy in pediatric subjects with epilepsy ≥ 4 years to < 17 years of age with partial-onset seizures. EP0034 will also be open to subjects who complete SP0967, which is the planned confirmatory study for LCM as adjunctive therapy in pediatric subjects with epilepsy aged ≥ 1 month to < 4 years with partial-onset seizures.

Dose selection in EP0034 is based on the primary studies (ie, SP0969 and SP0967). During EP0034, investigators will be allowed to increase or decrease the dose of LCM to optimize tolerability and seizure reduction for each subject. Lacosamide doses may be increased up to a maximum of LCM 600mg/day or 12mg/kg/day, whichever is lower based on body weight.

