6.3 Withdrawal criteria

Subjects are free to withdraw or the subject's legal representatives are free to withdraw the subject from the study at any time, without prejudice to their continued care.

Participation in this study **must** be discontinued for any of the following reasons:

1. Subject experiences intolerable AEs, including clinically relevant abnormal laboratory findings that, in the opinion of the investigator, preclude further participation in the study.
2. The sponsor or a regulatory agency requests withdrawal of the subject.
3. Subject has a QTc interval ≥ 500 ms that is confirmed by a cardiologist over read on any ECG.
4. Subject develops a second-degree atrioventricular (AV) block while awake or develops a third-degree AV block.
5. For subjects ≥ 6 years of age, subject has actual suicidal ideation since last visit as indicated by a positive response ("Yes") to either Question 4 or Question 5 of the C-SSRS. The subject should be referred immediately to a Mental Healthcare Professional and must be withdrawn from the study.
6. Subject is unwilling or unable to continue or legal representative is unwilling or unable to allow the subject to continue in the study.
7. Investigator decides that withdrawal from further participation would be in the subject's best interest.
9. Female subject who achieves menarche during the study and does not practice contraception as provided in Exclusion Criteria 5 unless sexually abstinent.

10. Subject becomes pregnant, as evidenced by a positive pregnancy test.

Participation in this study **may** be discontinued for any of the following reasons:

1. Any clinically relevant change in medical or psychiatric condition (if, in the opinion of the investigator, the condition warrants discontinuation from the study).
2. Subject requires a medication that is not permitted by the protocol (see Section 7.8.1).
3. Subject and/or legal representative is noncompliant with study procedures or medication, in the opinion of the investigator.

Subjects discontinuing LCM for any reason should taper off medication as described in Section 7.2.2. Whenever possible, these cases should be discussed with the Medical Monitor prior to withdrawing the subject from the study.

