7.2.1 Treatment Period

After completion of the Transition Period in the primary study, all subjects will have been transitioned to a dose of LCM according to their weight. Subjects will receive LCM 10mg/kg/day (oral solution) for subjects weighing <30kg, LCM 6mg/kg/day (oral solution) for subjects weighing ≥30kg to <50kg, and LCM 300mg/day (tablets) for subjects weighing ≥50kg during at least their first week in the Treatment Period of EP0034. After 1 week in EP0034, the investigator may adjust the LCM dose during the Treatment Period based on clinical judgment according to Table 7-1. If the investigator wants to adjust the LCM dosage after 1 week in EP0034, the subject should return to the clinic for an Unscheduled Visit, at the discretion of the investigator. Subjects who are able and willing to swallow tablets may be dispensed LCM tablets during the Treatment Period, based on clinical judgment, regardless of weight. Lacosamide doses may be increased up to a maximum of LCM 600mg/day or 12mg/kg/day, whichever is lower based on body weight.

Table 7-1: Minimum and maximum LCM dose during the Treatment Period

Formulation	Minimum LCM dose	Maximum LCM dose
Oral solution	2mg/kg/day	12mg/kg/day
Tablets	100mg/day	600mg/day

LCM=lacosamide

Subjects may be allowed to switch from one formulation to the other formulation during the Treatment Period based on clinical judgment. Consideration of the current LCM milligram dose in the oral solution should occur if/when transitioning to the tablet formulation. In cases where the LCM dose received with the oral solution is not supported by the tablet strengths available in EP0034 (50mg and 100mg), a clinical decision must be made by the investigator or other study physician to either increase or decrease the LCM dose to the next multiple of 50mg with a maximum permitted dose of 600mg/day.

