7.2.2 Taper Period

Subjects who withdraw during the study should taper off LCM if the following doses are achieved: LCM \geq 3mg/kg/day for subjects receiving LCM oral solution or LCM \geq 150mg/day for subjects taking tablets. It is recommended that the dose be tapered gradually in weekly decrements (see [Table 7-2](#) and [Table 7-3](#)). A slower taper is permitted, if medically necessary. In case of an emergency, a faster taper is permitted after discussion with the Medical Monitor, whenever possible.

Table 7-2: Dose taper steps for subjects receiving oral solution

LCM dose achieved	LCM doses for the Taper Period				
	Week 1	Week 2	Week 3	Week 4	Week 5
11 to 12mg/kg/day	9mg/kg/day	6mg/kg/day	4mg/kg/day	2mg/kg/day	–
9 to 10mg/kg/day	8mg/kg/day	6mg/kg/day	4mg/kg/day	2mg/kg/day	–
7 to 8mg/kg/day	6mg/kg/day	4mg/kg/day	2mg/kg/day	2mg/kg/day	–
5 to 6mg/kg/day	4mg/kg/day	2mg/kg/day	2mg/kg/day	–	–
3 to 4mg/kg/day	2mg/kg/day	2mg/kg/day	–	–	–

LCM=lacosamide

Table 7-3: Dose taper steps for subjects taking tablets

LCM dose achieved	LCM doses for the Taper Period				
	Week 1	Week 2	Week 3	Week 4	Week 5
>500 to 600mg/day	500mg/day	300mg/day	200mg/day	100mg/day	–
>400 to 500mg/day	400mg/day	300mg/day	200mg/day	100mg/day	–
>300 to 400mg/day	300mg/day	200mg/day	100mg/day	100mg/day	–
>200 to 300mg/day	200mg/day	100mg/day	100mg/day	–	–
≥150 to 200mg/day	100mg/day	100mg/day	–	–	–

LCM=lacosamide

Taper of LCM may not be required for some subjects who complete the study or withdraw from the study prematurely, depending on the treatment option selected by the investigator in consultation with the subject and/or legal representative(s) or for subjects who participate in EP0151 or EP0152.

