At the completion of the study, investigators should discuss treatment options with the subject and/or their legal representative(s) to best manage the subject's epilepsy. Taper of LCM may not be required for some subjects who complete the study, depending on the treatment option selected by the investigator in consultation with the subject and/or legal representative(s). These subjects should complete Visit 13/Termination Visit and then complete the Safety Follow-Up Telephone Contact 30 days (-1/+3 days) after the final dose of LCM. The Safety Follow-Up Visit is not required for subjects who complete the study and who do not undergo taper of LCM. The Safety Follow-Up Visit and the Safety Follow-Up Telephone Contact are not required for subjects who participate in EP0151 or EP0152.

Subjects who complete the study and discontinue use of LCM (as determined by the investigator in consultation with the subject and/or legal representative) should enter the Taper Period after the Visit 13/Termination Visit and taper LCM gradually as described in Section 7.2.2. A Taper Visit will be performed at the end of the Taper Period, followed by the Safety Follow-Up Visit that occurs 2 weeks (± 2 days) after the final dose of LCM, and then the Safety Follow-Up Telephone Contact that occurs 30 days (-1/+3 days) after the final dose of LCM.

Lacosamide for taper will be dispensed only for subjects who achieve a dose of LCM ≥ 3 mg/kg/day for subjects receiving oral solution, or LCM ≥ 150 mg/day for subjects taking tablets (Section 7.2.2). It is recommended that the dose be tapered gradually in weekly decrements. A slower taper is permitted, if medically necessary. In case of an emergency, a faster taper is permitted after discussion with the Medical Monitor, whenever possible.

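### The tablet taper rules carry no weight term, so a child of 33.3 kg or less ends the recommended tablet taper at 3 mg/kg/day or more, a dose that itself requires a taper on oral solution

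*Protocol*

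**What the plan says.** The taper trigger depends on dosage form. On oral solution it is 3 mg/kg/day. On tablets Protocol Section 5.1 sets 150 mg/day "for subjects taking tablets; lower doses will not require a taper". The same pair of triggers appears in Sections 1, 7.2.2, 8.1.12, 8.1.13 and 8.2, in the schedule footnotes, and in SAP Section 2.3.

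The supply of taper drug follows the same thresholds. Table 5-1 footnote s says "Lacosamide for taper will be dispensed only for subjects who achieve a dose of LCM" at or above them, and Section 8.1.12 repeats the rule. Section 6.3 says "Subjects discontinuing LCM for any reason should taper off medication as described in Section 7.2.2", which leads back to the same triggers.

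Section 7.2.2 has two schedules. Table 7-2 (solution) is in mg/kg/day and every row ends at 2 mg/kg/day. Table 7-3, headed "Dose taper steps for subjects taking tablets", is in mg/day, starts at 150 mg/day, and every row ends at 100 mg/day. Neither the tablet trigger nor Table 7-3 refers to body weight.

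Section 7.2.1 says that subjects able and willing to swallow tablets "may be dispensed LCM tablets during the Treatment Period, based on clinical judgment, regardless of weight". At the switch from solution, the physician is "to either increase or decrease the LCM dose to the next multiple of 50mg with a maximum permitted dose of 600mg/day". The tablet minimum is 100 mg/day (Table 7-1). The maximum does take account of weight: it is 600 mg/day or 12 mg/kg/day, "whichever is lower based on body weight" (Section 5.4).

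**The concern.** The tablet trigger of 150 mg/day equals the solution trigger of 3 mg/kg/day at one weight only, 50 kg. The tablet end point of 100 mg/day equals the solution end point of 2 mg/kg/day at that same weight. Children of 50 kg or more are the ones assigned tablets at entry, so the flat figures suit them. The protocol opens tablets to lighter children and leaves the taper rules unchanged.

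How gradually a light child with epilepsy is withdrawn from lacosamide by default then depends on dosage form. The Introduction reports the two forms as bioequivalent (single dose, healthy subjects), and the documents give no reason for treating them differently at withdrawal. The matter is patient safety at the end of treatment. It does not affect the efficacy analysis.

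**Working it through.** The plan states no figure to reproduce; the check is arithmetic on its dosing rules.

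**Inputs.** Triggers: 3 mg/kg/day and 150 mg/day (5.1). Tablet minimum 100 mg/day; maximum 12 mg/kg/day or 600 mg/day (7.2.1, Table 7-1). Tablet doses in multiples of 50 mg (7.2.1). Assigned dose: 10 mg/kg/day below 30 kg, 6 mg/kg/day from 30 to below 50 kg (7.2.1). Taper steps: Tables 7-2 and 7-3. The 15 kg lower limit used below is an assumption about who takes tablets; the protocol sets none.

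**Where the rules agree.** 150 / 3 = 50 kg for the trigger, and 100 / 2 = 50 kg for the last step.

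**Where the tablet taper ends at a dose that needs a taper on solution.** 100 mg/day equals 3 mg/kg/day at 100 / 3 = 33.3 kg. At 33.3 kg it is 3.003 mg/kg/day; at 33.4 kg it is 2.99. The 12 mg/kg/day cap sets the lower end of the range: 100 / 12 = 8.3 kg.

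**Schedules side by side (mg/kg/day).**

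| Weight and tablet dose | Dose per kg | Table 7-3 | Table 7-2 at the same dose |
|---|---|---|---|
| 15 kg, 150 mg/day | 10 | 6.7/6.7 (2 weeks) | 8/6/4/2 (4 weeks) |
| 20 kg, 200 mg/day | 10 | 5/5 (2 weeks) | 8/6/4/2 (4 weeks) |
| 25 kg, 250 mg/day | 10 | 8/4/4 (3 weeks) | 8/6/4/2 (4 weeks) |
| 30 kg, 150 mg/day | 5 | 3.3/3.3 (2 weeks) | 4/2/2 (3 weeks) |

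The 20 kg child stops from 5 mg/kg/day. On solution that dose would call for a further 4/2/2 over 3 weeks.

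**All weights from 15.0 to 29.9 kg at the assigned 10 mg/kg/day.** Take weights in 0.1 kg steps, round the dose down and up to 50 mg, and drop doses above 12 mg/kg/day. This leaves 273 weight-dose cases. The lowest dose after rounding is 150 / 19.9 = 7.5 mg/kg/day, so Table 7-2 always gives 4 weeks, whichever row an in-between dose uses. Table 7-3 gives 2 weeks at 150 or 200 mg/day (133 cases, 2 weeks shorter) and 3 weeks at 250 or 300 mg/day (140 cases, 1 week shorter). These are points on a weight scale, not children.

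**30.0 to 33.3 kg at the assigned 6 mg/kg/day (68 cases).** In-between doses matter here because Table 7-2 has gaps between rows. Giving them the lower row, 35 cases are 1 week shorter and 33 equal. Giving them the higher row, 34 are 2 weeks shorter and 34 are 1 week shorter.

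**The 100 mg/day group, if the dose achieved is the dose at stopping.** 100 mg/day is the only permitted tablet dose below the trigger. At 20 kg it is 5 mg/kg/day (solution: 4/2/2 over 3 weeks); at 25 kg it is 4 mg/kg/day (solution: 2/2 over 2 weeks). On tablets no taper is required. Reaching this dose from the assigned one means a cut of 33% at 15 kg (150 to 100 mg), 67% at 29.9 kg (299 to 100 mg), 44% at 30 kg (180 to 100 mg) and 50% at 33.3 kg (200 to 100 mg).

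**The case against.** **The key word is undefined.** A reader might infer that the protocol plainly leaves light children on 100 mg/day tablets with no taper. The text does not establish that. Every child below 50 kg is assigned 6 or 10 mg/kg/day of solution for at least the first week, so if the trigger means the highest dose ever reached, these children have met it and the gap closes. That meaning works badly for choosing a table row: a 20 kg child once on 10 mg/kg/day and now on 5 would rise to 8 in taper Week 1. This does not prove that the trigger means the dose at stopping. The objection stands against the 100 mg/day gap. It does not touch the shorter schedule or the 100 mg/day end point, which apply at 150 mg/day and above on either reading.

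**The thresholds have a visible logic.** Each trigger sits one step above its form's minimum dose, and each table ends at that minimum. This may explain where the figures came from. It does not make 100 mg/day a low dose at 20 kg.

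**Investigators have discretion.** The steps are recommendations, a slower taper is permitted if medically necessary, and doses can be reduced by telephone (8.1.2). This is a real safeguard at 150 mg/day and above. It does not change the default, and solution users have the same discretion together with a weight-based default.

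**Few children may be affected.** For the 100 mg/day group this is fair, since it needs a low weight, a switch to tablets, a large dose cut and then a stop. The shorter schedule needs only a permitted switch, but its frequency is unknown too. Children who continue lacosamide or enter EP0151 or EP0152 may need no taper.

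**Conclusion.** The point holds, led by the mismatch in default schedules. At 33.3 kg or less, the recommended tablet taper ends at 3 mg/kg/day or more, which is at or above the protocol's own solution threshold for needing a taper. From 15.0 to 29.9 kg at the assigned dose switched to tablets, it is also 1 to 2 weeks shorter than Table 7-2; from 30.0 to 33.3 kg it is 0 to 2 weeks shorter, depending on rounding and row. The missing taper and taper supply at 100 mg/day is conditional on the dose achieved meaning the dose at stopping, and probably concerns few children.

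A reader might also infer that the tablet schedule causes withdrawal seizures. The documents do not say how much a shorter taper raises seizure risk, so no such claim is made. The result rests on the documents' dosing rules, on the assumed 15 kg lower limit, and on no information about how many light children take tablets. This is a cheap improvement to a safety procedure.

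**What to change.** 1. In Protocol Sections 5.1, 7.2.2, 8.1.12, 8.1.13 and 8.2 and the matching footnotes (Table 5-1 s, Table 5-2 r, Table 5-3 a), with Section 1 and SAP Section 2.3 aligned, set the tablet trigger for taper and for taper supply at 150 mg/day or more, or 3 mg/kg/day or more by latest body weight, whichever is lower. State that the dose achieved means the dose at the time of stopping.
2. State that a tablet taper should not end at 3 mg/kg/day or more. Where 100 mg/day is 3 mg/kg/day or more, continue on oral solution down to 2 mg/kg/day, with the Table 7-2 steps as the guide. The sponsor's clinical team should confirm the steps so that taper length does not jump at 33.3 kg. Simply substituting Table 7-2 below that weight would create a jump: on 200 mg/day, a child of 33.3 kg (6.006 mg/kg/day, higher row) would get 4 weeks and a child of 33.4 kg would get 2.

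**Cost.** The new trigger alters one tablet dose, 100 mg/day, at 33.3 kg or less. The second change affects the end of the taper at every tablet dose in that weight range. Weight is already measured at each visit, SAP Section 3.2.8 already converts tablet doses to mg/kg/day by latest weight, and 10 mg/mL solution is already supplied. At 20 kg, a 4/2/2 taper from 100 mg/day uses (80 + 40 + 40) × 7 / 10 = 112 mL; a full 8/6/4/2 taper from 200 mg/day uses (160 + 120 + 80 + 40) × 7 / 10 = 280 mL. The downsides are a change of form during withdrawal and, for a few children, a Taper Visit and possibly a Safety Follow-Up Visit.

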5.1.1 Study duration per subject

The maximum duration of LCM administration during EP0034 will be approximately 2 years.

The start of the study is defined as the first visit of the first subject entering the study. The end of the study is defined as the date of the last telephone contact (or last site visit if telephone contact does not happen) of the last subject in the study.

5.1.2 Planned number of subjects and site(s)

Approximately 500 subjects from SP0967 and SP0969 may be eligible to enroll in this open-label extension study. The number of sites is dependent on the number of enrolling centers from SP0967 and SP0969.

5.1.3 Anticipated regions and countries

The study will be conducted in North America, Europe, Latin America, and the Asia/Pacific regions, with the possibility to expand the study to other countries and regions if deemed necessary.

5.2 Schedule of study assessments

Table 5-1, Table 5-2 and Table 5-3 present the tabular schedules of study procedures.

Table 5-1: Schedule of study assessments: Treatment Period up to Week 28

Assessments	Treatment Period ^a											ETV ^b	Unsch Visit ^c
	V1	TC1	V2	TC2	V3	TC3	V4	TC4	V5	TC5	V6		
	W0	W2	W4	W6	W8	W10	W12	W16	W20	W24	W28		
Informed consent	X												
Inclusion/exclusion criteria	X												
Medical history update	X												
Concomitant medications	X ^d	X	X	X	X	X	X	X	X	X	X	X	X
Concomitant AEDs	X ^d	X	X	X	X	X	X	X	X	X	X	X	X
VNS assessment ^e	X ^d		X		X		X		X		X	X	X
Physical examination (complete)	X ^d								X			X	
Physical examination (brief)			X		X		X				X		
Tanner Stage ^f	X ^g								X			X	
Blood pressure and pulse rate (including orthostatic assessments in ambulatory subjects)	X ^d		X		X		X		X		X	X	X
Body weight and height	X ^d		X		X		X		X		X	X	X ^h
Head circumference	X ^g								X			X	
Neurological examination (complete)	X ^d								X			X	
Neurological examination (brief)			X		X		X				X		
12-lead ECG ⁱ	X ^g		X								X	X	
Clinical chemistry and hematology blood sample	X ^d								X			X	
Endocrinology blood sample	X ^g								X			X	
Urinalysis (subjects aged ≥5 years) ^j	X ^d								X			X	

Table 5-1: Schedule of study assessments: Treatment Period up to Week 28

Assessments	Treatment Period ^a											ETV ^b	Unsch Visit ^c
	V1	TC1	V2	TC2	V3	TC3	V4	TC4	V5	TC5	V6		
	W0	W2	W4	W6	W8	W10	W12	W16	W20	W24	W28		
Serum pregnancy test ^k									X			X	
Urine pregnancy test ^k	X ^d		X		X		X				X		
C-SSRS ^l	X ^d		X		X		X		X		X	X	X ^m
Clinical GIC									X			X	
Caregiver GIC									X			X	
Achenbach CBCL ⁿ	X								X			X	
Bayley-III ^o	X ^d								X			X	
BRIEF/BRIEF-PP	X								X			X	
PedsQL ^q	X ^g								X			X	
Contact IXRS	X		X		X		X		X		X	X ^r	
LCM return/compliance	X ^d		X		X		X		X		X	X	
Dispense LCM	X		X		X		X		X		X	X ^s	
Subject diary ^t	X ^d	X	X	X	X	X	X	X	X	X	X	X	X
Withdrawal criteria		X	X	X	X	X	X	X	X	X	X		X
AE reporting ^u	X ^d	X	X	X	X	X	X	X	X	X	X	X	X
Health care resource use	X ^d		X		X		X		X		X	X	

AE=adverse event; AED=antiepileptic drug; Bayley-III=Bayley Scales of Infant and Toddler Development, Third Edition; BRIEF-P/BRIEF=Behavior Rating Inventory of Executive Function-Preschool Version/Behavior Rating Inventory of Executive Function; CBCL=Child Behavior Checklist; C_{max}=maximum plasma concentration; C-SSRS=Columbia-Suicide Severity Rating Scale; ECG=electrocardiogram; ETV=Early Termination Visit; GIC=Global Impression of Change; IXRS=interactive voice/web response system; LCM=lacosamide; PedsQL=Pediatric Quality of Life Inventory; TC=telephone contact; Unsch=Unscheduled; V=Visit; VNS=vagus nerve stimulation; W=week

Table 5-1: Schedule of study assessments: Treatment Period up to Week 28

Assessments	Treatment Period ^a											ETV ^b	Unsch Visit ^c
	V1	TC1	V2	TC2	V3	TC3	V4	TC4	V5	TC5	V6		
	W0	W2	W4	W6	W8	W10	W12	W16	W20	W24	W28		

^a A time window of ± 7 days relative to Visit 1 is applicable for all scheduled visits and telephone contacts after Visit 1 during the Treatment Period.

^b An Early Termination Visit must be completed for all subjects who prematurely discontinue from the study.

^c If an Unscheduled Visit is needed, then the assessments noted will be performed. Additional assessments can be performed at the investigator's discretion.

^d Assessments may have already been completed during the final Transition Visit of the primary study (SP0969 or SP0967) and should not be repeated at Visit 1 of EP0034.

^e Only applicable for subjects with an implanted VNS device.

^f The Tanner Stage will be performed only for subjects who are pubescent at V1 or who enter puberty during the course of the study.

^g Assessments may have already been completed during the final Maintenance Visit of the primary study (SP0969 or SP0967) and should not be repeated at Visit 1 of EP0034.

^h Height will not be recorded at an Unscheduled Visit.

ⁱ A 12-lead ECG (2 interpretable recordings approximately 20 to 30 minutes apart) will be performed prior to any blood draws and vital signs and, if possible, after the subject has been in a supine position for approximately 5 minutes preceding the ECG recording. All subjects will be required to have a 12-lead ECG (2 interpretable recordings approximately 20 to 30 minutes apart) conducted at LCM C_{max} 1 week after a LCM dose increase to ≥ 8 mg/kg/day, after subsequent dose increases (ie, the first time a subject reaches a LCM dose of 8mg/kg/day, 9mg/kg/day, 10mg/kg/day, etc) or for LCM doses of ≥ 400 mg/day (ie, the first time a subject reaches a LCM dose of 400mg/day, 500mg/day, etc), or when a new concomitant AED is introduced during the study. This ECG can be conducted at an Unscheduled Visit, if necessary. Subjects having a LCM dose increase to ≥ 8 mg/kg/day or to ≥ 400 mg/day, or when a new concomitant AED is added, will be required to arrive at the clinic prior to taking their morning dose of LCM. Subjects will be administered their morning LCM dose by study personnel at the clinic so that an ECG (2 interpretable recordings approximately 20 to 30 minutes apart prior to any blood sample collection or vital signs assessment) can be performed 30 minutes to 1 hour after the administration of LCM.

^j For subjects aged ≥ 5 years, urine assessments will be based on the subject's ability to void and staff's ability to collect urine (in an appropriate container).

^k For female subjects of childbearing potential.

^l For all subjects ≥ 6 years of age, the "Since Last Visit" version of the C-SSRS should be completed. If a subject becomes 6 years of age during the study, the "Already Enrolled" version of the C-SSRS should be used at the first visit at which the subject is 6 years of age and the "Since Last Visit" version at subsequent visits.

^m The C-SSRS assessment should be completed if the Unscheduled Visit is due to a safety or efficacy reason.

ⁿ The version of the Achenbach CBCL appropriate to each subject's age should be administered with the following exception: For subjects who completed the CBCL/1½-5 at the Baseline assessment of the primary study and turn 6 years of age within 1 year after the Baseline assessment of the primary study, the CBCL/1½-5 should be completed for 1 year after the Baseline assessment of the primary study, and subsequently the CBCL/6-18 should be completed. The Achenbach CBCL will only be administered in countries where a validated translated version is available.

^o The Bayley-III scales should be completed for subjects < 18 months of age at study entry if enrolled in English-speaking countries. The same scale should be completed for 1 year after the Baseline assessment of the primary study, even if the subject turns > 18 months of age during that period.

^p The BRIEF-P or BRIEF appropriate for each subject's age should be completed, with the following exception: For subjects who completed the BRIEF-P at the

Table 5-1: Schedule of study assessments: Treatment Period up to Week 28

Assessments	Treatment Period ^a											ETV ^b	Unsch Visit ^c
	V1	TC1	V2	TC2	V3	TC3	V4	TC4	V5	TC5	V6		
	W0	W2	W4	W6	W8	W10	W12	W16	W20	W24	W28		

Baseline assessment of the primary study and turn 5 years of age within 1 year after the Baseline assessment of the primary study, the BRIEF-P should be completed for 1 year after the Baseline assessment of the primary study, and subsequently the BRIEF should be completed. The BRIEF-P and BRIEF will only be administered in countries where a validated translated version is available.

^q The PedsQL form appropriate for each subject's age should be completed, with the following exception: If a subject ages up to the next form of the PedsQL within 1 year after the Baseline assessment of the primary study, the form that was used at the Baseline assessment should be completed for 1 year after the Baseline assessment of the primary study, and subsequently the form consistent with his/her age at the time of assessment should be completed. The PedsQL will only be administered in countries where a validated translated version is available.

^r Only if LCM will be dispensed for taper.

^s Lacosamide for taper will be dispensed only for subjects who achieve a dose of LCM ≥ 3 mg/kg/day (oral solution) or LCM ≥ 150 mg/day (tablet). It is recommended that the dose be tapered gradually in weekly decrements. A slower taper is permitted, if medically necessary. In case of an emergency, a faster taper is permitted after discussion with the Medical Monitor, whenever possible. Taper of LCM may not be required for some subjects who withdraw from the study prematurely, depending on the treatment option selected by the investigator in consultation with the subject and/or legal representative(s).

^t Subjects and/or legal representative(s) will be reminded to complete the diary on a daily basis.

^u Ongoing AEs from the primary study will be followed, as well as recording of new AEs during the current study.

Table 5-2: Schedule of study assessments: Treatment Period from Week 32 to Week 96/Termination Visit

Assessments	Treatment Period ^a													ETV ^b	Unsch Visit ^c	
	TC6	V7	TC7	V8	TC8	V9	TC9	V10	TC10	V11	TC11	V12	V13 / TermV ^d			
	W32	W36	W40	W44	W48	W52	W56	W60	W66	W72	W78	W84	W96			
Concomitant medications	X	X	X	X	X	X	X	X	X	X	X	X	X	X	X	X
Concomitant AEDs	X	X	X	X	X	X	X	X	X	X	X	X	X	X	X	X
VNS assessment ^e		X		X		X		X		X		X	X	X	X	X
Physical exam (complete)						X							X	X		
Physical exam (brief)		X		X				X		X		X				
Tanner Stage ^f						X							X	X		
Blood pressure and pulse rate (including orthostatic assessments in ambulatory subjects)		X		X		X		X		X		X	X	X	X	X
Body weight and height		X		X		X		X		X		X	X	X	X	X ^g
Head circumference						X				X			X	X		
Neurological exam (complete)						X							X	X		
Neurological exam (brief)		X		X				X		X		X				
12-lead ECG ^h						X				X			X	X		
Clinical chemistry and hematology blood sample						X				X			X	X		

Table 5-2: Schedule of study assessments: Treatment Period from Week 32 to Week 96/Termination Visit

Assessments	Treatment Period ^a													ETV ^b	Unsch Visit ^c
	TC6	V7	TC7	V8	TC8	V9	TC9	V10	TC10	V11	TC11	V12	V13 / TermV ^d		
	W32	W36	W40	W44	W48	W52	W56	W60	W66	W72	W78	W84	W96		
Endocrinology blood sample						X				X			X	X	
Urinalysis (subjects aged ≥5 years) ⁱ						X				X			X	X	
Serum pregnancy test ^j						X				X			X	X	
Urine pregnancy test ^j		X		X				X				X			
C-SSRS ^k		X		X		X		X		X		X	X	X	X ^l
Clinical GIC						X				X			X	X	
Caregiver GIC						X				X			X	X	
Achenbach CBCL ^m						X				X			X	X	
Bayley-III ⁿ						X				X				X	
BRIEF/BRIEF-P ^o						X				X			X	X	
PedsQL ^p						X				X			X	X	
Contact IXRS		X		X		X		X		X		X	X ^q	X ^p	
LCM return/compliance		X		X		X		X		X		X	X	X	
Dispense LCM		X		X		X		X		X		X	X ^r	X ^q	
Subject diary ^s	X	X	X	X	X	X	X	X	X	X	X	X	X	X	X
Withdrawal criteria	X	X	X	X	X	X	X	X	X	X	X	X			X
AE reporting	X	X	X	X	X	X	X	X	X	X	X	X	X	X	X

Table 5-2: Schedule of study assessments: Treatment Period from Week 32 to Week 96/Termination Visit

Assessments	Treatment Period ^a													ETV ^b	Unsch Visit ^c
	TC6	V7	TC7	V8	TC8	V9	TC9	V10	TC10	V11	TC11	V12	V13 / TermV ^d		
	W32	W36	W40	W44	W48	W52	W56	W60	W66	W72	W78	W84	W96		
Health care resource use		X		X		X		X		X		X	X	X	

AE=adverse event; AED=antiepileptic drug; Bayley-III=Bayley Scales of Infant and Toddler Development, Third Edition; BRIEF-P/BRIEF=Behavior Rating Inventory of Executive Function-Preschool Version/Behavior Rating Inventory of Executive Function; CBCL=Child Behavior Checklist; C_{max}=maximum plasma concentration; C-SSRS=Columbia-Suicide Severity Rating Scale; ECG=electrocardiogram; ETV=Early Termination Visit; GIC=Global Impression of Change; IXRS=interactive voice/web response system; LCM=lacosamide; PedsQL=Pediatric Quality of Life Inventory; TC=telephone contact; TermV=Termination Visit; Unsch=Unscheduled; V=Visit; VNS=vagus nerve stimulation; W=week

^a A time window of ± 7 days relative to Visit 1 is applicable for all scheduled visits and telephone contacts after Visit 1 during the Treatment Period.

^b An Early Termination Visit must be completed for all subjects who prematurely discontinue from the study.

^c If an Unscheduled Visit is needed, then the assessments noted will be performed. Additional assessments can be performed at the investigator's discretion.

^d Visit 13 will be the treatment Termination Visit for subjects who complete up to 2 years of treatment.

^e Only applicable for subjects with an implanted VNS device.

^f The Tanner Stage will be performed only for subjects who are pubescent at V1 or who enter puberty during the course of the study.

^g Height will not be recorded at an Unscheduled Visit.

^h A 12-lead ECG (2 interpretable recordings approximately 20 to 30 minutes apart) will be performed prior to any blood draws and vital signs and, if possible, after the subject has been in a supine position for approximately 5 minutes preceding the ECG recording. All subjects will be required to have a 12-lead ECG (2 interpretable recordings approximately 20 to 30 minutes apart) conducted at LCM C_{max} 1 week after a LCM dose increase to ≥ 8 mg/kg/day, after subsequent dose increases (ie, the first time a subject reaches a LCM dose of 8mg/kg/day, 9mg/kg/day, 10mg/kg/day, etc) or for LCM doses of ≥ 400 mg/day (ie, the first time a subject reaches a LCM dose of 400mg/day, 500mg/day, etc), or when a new concomitant AED is introduced during the study. This ECG can be conducted at an Unscheduled Visit, if necessary. Subjects having a LCM dose increase to ≥ 8 mg/kg/day or to ≥ 400 mg/day, or when a new concomitant AED is added will be required to arrive at the clinic prior to taking their morning dose of LCM. Subjects will be administered their morning LCM dose by study personnel at the clinic so that an ECG (2 interpretable recordings approximately 20 to 30 minutes apart prior to any blood sample collection or vital signs assessment) can be performed 30 minutes to 1 hour after the administration of LCM.

ⁱ For subjects aged ≥ 5 years, urine assessments will be based on the subject's ability to void and staff's ability to collect urine (in an appropriate container).

^j For female subjects of childbearing potential.

^k For all subjects ≥ 6 years of age, the "Since Last Visit" version of the C-SSRS should be completed. If a subject becomes 6 years of age during the study, the "Already Enrolled" version of the C-SSRS should be used at the first visit at which the subject is 6 years of age and the "Since Last Visit" version at subsequent visits.

^l The C-SSRS assessment should be completed if the Unscheduled Visit is due to a safety or efficacy reason.

Table 5-2: Schedule of study assessments: Treatment Period from Week 32 to Week 96/Termination Visit

Assessments	Treatment Period ^a													ETV ^b	Unsch Visit ^c
	TC6	V7	TC7	V8	TC8	V9	TC9	V10	TC10	V11	TC11	V12	V13 / TermV ^d		
	W32	W36	W40	W44	W48	W52	W56	W60	W66	W72	W78	W84	W96		

